 1. ONLS
 2. Timed 10-meter walk test
 3. MRC
 4. INCAT sensory score
 5. 6-minute walk test
 6. Posturometry
- Anti-MAG group:
 1. ONLS
 2. INCAT sensory score
 3. Timed 10-meter walk test
 4. MRC
 5. Posturometry
 6. 6-minute walk test
- CMT-1a and CMT-1b:
 1. ONLS
 2. MRC
 3. Timed 10-meter walk test
 4. 6-minute walk test
 5. INCAT sensory score
 6. Posturometry

Regarding the electrophysiological testing, the secondary endpoints will be ranked as follows:

1. Supernormality (%)
2. Strength-duration time constant (ms)
3. Rheobase (mA)
4. Refractoriness (%)
5. Min-max absolute refractory period (ms)

The secondary endpoints are changes from baseline to week 48 in ONLS, MRC, INCAT, Posturometry, Timed 10-meter walk test, 6-min walk test, Min-max absolute refractory period, Refractoriness, Supernormality, Strength-duration time constant, Rheobase

Secondary objective:

The evaluation endpoint is the proportion of patients with WHO grade III adverse events.

7.1.6 Safety analyses

All treated patients will be included in the safety analysis. All safety data will be displayed and analyzed using descriptive statistical methods. No formal statistical analysis is planned.

Time of the analyses

Safety data will be reviewed on a regular basis by the DSMB.

A complete safety analysis as described below will be performed at the time the primary efficacy endpoint is analysed. After withdrawal or completion of the study by all included patients, whole or part of the safety analyses will be performed again. The details of these final analyses will be given in the SAP.

Adverse events

In general, analysis of adverse events is descriptive.

Statistical analysis and reporting of adverse events will concentrate on treatment emergent adverse events. All adverse events with an onset after the first dose of biotin up to a certain number of days (D) (inclusive) after the last dose of biotin will be considered 'treatment emergent' and will be assigned to the treatment phase for evaluation. The number of days D will be given in the SAP. Adverse events that start before first drug intake and deteriorate under treatment will also be considered as 'treatment-emergent'. Other adverse events will be assigned either to the screening or safety follow-up, or post study phase, as appropriate.

Vital signs, physical exam, standard laboratory tests

The set of summary statistics will be n (number of patients with non-missing values), mean, standard deviation (SD), minimum, maximum, median and interquartile range, and will be n (number patient with non-missing values) and percentage (%) for continuous and categorical endpoints, respectively.

7.1.7 Analysis by subgroups

Analyses in subgroups will be performed in order to assess the homogeneity of treatment's effect as exploratory analyses.

7.1.8 Handling of missing data

Missing data due to dropouts may occur for two major classes of reasons: non-informative reasons (essentially random, e.g., a study subject moves to another city) and informative reasons (essentially non-random, and possibly related to treatment assignment or outcomes, e.g., the study subject develops intolerable side effects).

The last observation carried forward (LOCF) approach will be used to handle missingness on the primary evaluation criterion.

7.1.9 Handling of changes in planned statistical analyses

The Statistical Analyses Plan will be validated with the principal investigator prior the data base lock at which the primary efficacy endpoint will be analysed. Any later modification will be described in a complementary SAP.

8 PRESTUDY DOCUMENTATION

The investigator must provide the sponsor with the following documents BEFORE enrolling any patients:

- Completed and signed statement of investigator form (i.e., FDA form 1572 or Alternate 1572 form, if required by local regulations, an equivalent).

- All applicable country-specific regulatory forms.
- Current signed and dated curriculum vitae for the principal investigator, sub-investigators, determination of eligibility, efficacy, or safety) who are listed on the statement of investigator form (i.e., FDA form 1572 or Alternate 1572 form and, if required by local regulations, an equivalent).
- Copy of the IRB/IEC approval letter for the protocol and informed consent. All advertising, recruitment, and other written information provided to the patient must be approved by the IRB/IEC. Written assurance of continuing approval (at least annually) and, where required, a copy of the annual progress report submitted to the IRB/IEC must also be provided to the sponsor.
- Copy of the IRB/IEC-approved informed consent document to be used.
- If applicable, a list of the IRB/IEC members and their qualifications and a description of the committee's working procedure.
- Copy of the protocol sign-off page signed by the investigator.
- Fully executed CSA.
- If applicable, a financial disclosure form.
- A written document containing the name, location, certification number, and date of certification of the laboratory to be used for laboratory assays and those of other facilities conducting tests. This document should be returned along with the statement of investigator form. The sponsor must be notified if the laboratory is changed or if any additional laboratory is to be used.
- List of normal laboratory values and units of measure for all laboratory tests required by the protocol. This is required for each laboratory to be used during the study. The sponsor/designee must be notified if normal values or units of measurement change.

9 INFORMED CONSENT

The investigator will provide for the protection of the patients by following all applicable regulations. These regulations are available upon request from the sponsor or designee. The informed consent document(s) used during the informed consent process must be reviewed by the sponsor, approved by the IRB/IEC, and available for inspection.

Before any protocol-required procedures are performed, a patient must:

- Be informed of all pertinent aspects of the study and elements of informed consent.
- Be given time to ask questions and time to consider the decision to participate.
- Voluntarily agree to participate in the study.
- Sign and date an IRB/IEC-approved informed consent document.

The investigator must explain to each patient (or legally authorised representative) the nature of the study, its purpose, the procedures involved, the expected duration, the potential risks and benefits involved and any discomfort it may entail. Each subject must be informed that participation in the study is voluntary and that he/she may withdraw from the study at any time and that withdrawal of consent will not affect his/her subsequent medical treatment or relationship with the treating physician.

This informed consent should be given by means of a standard written statement, in non-technical language. The subject should read and consider the statement before signing and dating it, and should be given a copy of the signed document.

10 DIRECT ACCESS, DATA HANDLING AND RECORD-KEEPING**10.1 Investigator**

The investigator will permit study-related monitoring, audits, IRB/IEC review, and regulatory inspections by providing direct access to source data and documents.

All information will be recorded on source documents. The CRFs must be fully completed and include all required data. All CRF data must be submitted to the sponsor throughout and at the end of the study. Remote data capture will be used to record and transmit data electronically to the sponsor or designee.

If an investigator retires, relocates, or otherwise withdraws from conducting the study, the investigator must notify the sponsor to agree upon an acceptable storage solution. Regulatory agencies will be notified with the appropriate documentation. An updated statement of investigator form (i.e., US Food and Drug Administration [FDA] form 1572 or Alternate 1572 form if required by local regulations, an equivalent) will be filed with the sponsor or designee for any changes in the study personnel reported in the current statement of investigator form.

Investigators must notify their IRB/IEC of protocol violations in accordance with local regulatory and IRB/IEC requirements.

The investigator will allow the monitor to visit the site facilities where the study will take place in order to ensure that the site complies with the requirements of the protocol and the GCP.

10.2 Sponsor

The CRF data are stored in a database and processed electronically. The sponsor or designee reviews the data for safety information. The data are reviewed for legibility, completeness, and logical consistency. Automated validation programs identify missing data, out-of-range data, and other data inconsistencies. Requests for data clarification are forwarded to the investigative site for resolution.

At regular intervals during the study, the monitor will visit the site, to check the completeness of patients' records, the accuracy of entries on the CRF, the adherence to protocol and to Good Clinical Practice, the progress of enrolment, and to ensure that study medication is being stored and accounted for according specifications.

The investigator and key trial personnel must be available to assist the monitor during these visits.

10.3 Source document requirements

The investigator must give the monitor direct access to relevant hospital or clinical records, to confirm their consistency with the CRF data entries.

The consent form will include a statement by which the patients allows the sponsor's duly authorized personnel (trial monitoring team) to have direct access to source data which supports data on the electronic case report forms. These personnel, bound by professional secrecy, will not disclose any personal identity or personal medical information.

10.4 The use and completion of electronic Case Report Forms (CRFs)

It is responsibility of the Investigator to maintain adequate and accurate CRFs in recording all observations and other data pertinent to the clinical investigation on ongoing basis into the CRFs designed by an CRF provider.

CRFs are implemented electronically (CRF), using third party software application that is fully validated and conforms to regulatory requirements for electronic data capture, where applicable.

The CRF enables data capture via an on-line system on a personal computer (PC).

- Designated staff at participating site shall enter data required by the protocol into the CRF.
- All access to the system is administered by the CRF administrator, and will only be granted after appropriate and documented training. A dedicated account (with login and password) will be provided at each user by the CRF administrator.
- Specific guidelines for data completion will be available.
- The data will be recorded via the application into a central database over encrypted lines using the SSL (Secure Sockets Layer) protocol.
- Personal health identifiers are stored in the central database in encrypted form.
- All entries and modifications of data are logged in an audit trail.
- Electronic signatures will be used where required.
- Automated validation program check for data discrepancies in the CRFs will be implemented where appropriate.

11 ADMINISTRATIVE RULES

11.1 Curriculum vitae

An updated copy of the curriculum vitae of the investigator will be provided to the sponsor prior to the beginning of the study.

11.3 Protocol amendments

Any change in the study plan requires a protocol amendment. An investigator must not make any changes to the study without IRB/IEC and sponsor approval except when necessary to eliminate apparent immediate hazards to the subjects. A protocol change intended to eliminate an apparent immediate hazard to subjects may be implemented immediately, but the change must then be documented in an amendment, reported to the IRB/IEC within 5 working days, and submitted to the appropriate regulatory agency in the required time frame.

All protocol amendments must be reviewed and approved by the sponsor and investigator.

11.4 Record retention in investigation centre(s)

The investigator shall retain and preserve 1 copy of all data collected or databases generated in the course of the study, specifically including but not limited to those defined by GCP as essential, for the longer of (a) 2 years after the last marketing authorization for the study drug has been approved or the sponsor has discontinued its research with respect to such drug or (b) such longer period as required by applicable global regulatory requirements. At the end of such period, the investigator shall notify the sponsor in writing of his or her intent to destroy all such material. The sponsor shall have 30 days to

respond to the investigator's notice, and the sponsor shall have a further opportunity to retain such materials at the sponsor's expense.

11.5 Insurance compensation

The sponsor certifies having taken out a liability insurance policy which covers the investigators and his co-workers and which is in accordance with the local laws and requirements.

A certificate of insurance will be provided to the investigator.

11.6 Quality control and assurance

The sponsor or designee performs quality control and assurance checks on all clinical studies that it sponsors. Before enrolling any subjects in this study, sponsor personnel or designee and the investigator review the protocol, the investigator's brochure, the CRFs and instructions for their completion, the procedure for obtaining informed consent, and the procedure for reporting AEs and SAEs. A qualified representative of the sponsor will monitor the conduct of the study. During these site visits, information recorded in the CRFs is verified against source documents.

11.7 Ownership of results - Publication

The results from this study are the exclusive property of the sponsor.

No information concerning the study or its results may be published or communicated without the prior written and signed agreement of the sponsor.

The sponsor's decision to publish or otherwise publicly communicate the results of this study will be made in accordance with all applicable laws, regulations, and sponsor policies regarding publication and communication of clinical study results.

11.8 Study-specific committees

11.8.1 Scientific and Steering committee to be updated

Members: [name] [name], [name] [name]

Mission: defining the objective, compiling the protocol, and proposing protocol amendments during the study.

Defining the general organization of the study, coordinating the information, initially determining the methodology, and monitoring implementation of the study.

Proposing management during the study taking into account the recommendations of the data safety monitoring board (DSMB), if appropriate.

11.8.2 Data Safety Monitoring Board (DSMB)

Members: Pr [name], Pr [name], Pr [name]

DSMB's mission is 1) to ensure throughout the study the safety of patients involved in the study, and 2) to preserve the scientific and ethical integrity of the study. DSMB is an advisory committee to provide the sponsor for its biomedical research advice and recommendations on the conduct of the study.

DSMB can help sponsor and investigators of the study to be taken during the study for which decisions independent judgment is desirable. DSMB may for this purpose:

- Recommend further analysis to the interpretation of the results of an interim review of data ;

- Recommend minor or major modifications of the protocol became necessary because of recruitment, or follow-up testing or, to take account of new scientific data ;
- Recommend early termination of the trial.

In case of occurrence of SAEs attributable to experimental treatment, the DMSB will be seized by the investigator and / or sponsor to decide on the continuation of the trial.

13 APPENDICES

Appendix 1:

Biological testing biotin may interfere with (non-exhaustive list):

ANAEMIA	Tg	Tacrolimus	Procalcitonin
Ferritin	TSH	Theophylline	TNF- α
Folate	T-Uptake	Tobramycine	Transferrin
Vitamin B12	INFECTIOUS	Vancomycine	
CARDIOLOGY	Ag HBe	BONE	
CK-MB	Ag HBs	METABOLISM	
Myoglobin	Anti-HAV	Anti CCP	
Nt-proBNP 2	Anti-HBc	Beta cross Laps	
Troponin I	Anti-HBc IgM	Osteocalcin	
Troponin T	Anti-Hbe	PTH	
HORMONES /	Anti-HBs	P1NP	
FERTILITY	Anti-HCV 2	Vitamin D	
ACTH	CMV IgG, IgM	ONCOLOGY	
AMH	HIV Ag p24	ACE	
Cortisol	HIV Ag Confirm.	AFP	
C-Peptide	HIV Combi PT	CA 125	
DHEA-s	HSV-1/2 IgG	CA 15-3	
Estradiol	Rubella IgG, IgM	CA 19.9	
FSH, LH	Syphilis	CA 72-4	
HCG	Toxo Avidity	Cyfra 21-1	
hGH	Toxo IgG, IgM	HE4	
Insulin	DRUGS	HER-2/neu	
PAPP-A	Carbamazepine	NSE	
PIGF	Ciclosporine	ProGRP	
Progesterone	Digitoxine	PSA	
Prolactin	Digoxine	S100	
SHBG	Gentamicine	sFlt-1	
Testosterone	Lidocaine	TPS	
THYROID	Lithium	SEPSIS /	
Anti TG	Mycophenolate	INFLAMMATION	
Anti TPO	Phenobarbital	C3, C4	
Anti-TSHr	Phenytoine	CRP	
Calcitonin	Procainamide	IgA IgE IgG IgM	
T3, FT3	Sirolimus	IL6 IL8 IL10	
T4, FT4	Sodium Valproate	LBP	
		Prealbumin	

Appendix 2

Medical Research Council (MRC) sum score

The total MRC sum score ranges from 0 (total paralysis) to 60 (normal strength). The score is the sum of the MRC score of 6 muscles (3 at the upper and 3 at the lower limbs) on both sides, each muscle graded from 0 to 5. The following muscles are examined:

- Deltoid
- Biceps
- Wrist extensor
- Iliopsoas
- Quadriceps femoris
- Tibialis anterior

MRC-Muscle Grading Scale

Grade	Degree of Strength
5	Normal Strength
4	Ability to resist against moderate pressure throughout range of motion
3	Ability to move through full range of motion against gravity. If a subject has a contracture that limits joint movement, the mechanical range will be to the point at which the contracture causes joint restriction
2	Ability to move through full range of motion with gravity eliminated
1	A flicker of motion is seen or felt in the muscle
0	No movement

Kleyweg RP, van der Mechè FGA, Schmitz PIM. Interobserver agreement in the assessment of muscle strength and functional abilities in Guillain-Barré syndrome. *Muscle Nerve* 1991;14:1103-1109.

Medical Research Council sum Score: Grille d'évaluation

Coter chaque muscle des deux côtés selon la règle suivante:

Grade	Force
5	Force normale
4	Mouvement possible contre résistance modérée
3	Mouvement possible contre gravité. L'étendue du mouvement s'entend jusqu'au point où une contracture bloque l'articulation.
2	Mouvement possible si la gravité est neutralisée.
1	Ebauche de mouvement vue ou palpable dans le muscle
0	Aucun mouvement

Muscle	Grade	
	Droit	Gauche
Deltoïde		
Biceps		
Extenseurs du poignet		
Psoas		
Quadriceps		
Jambier antérieur		
Total		
SOMME DES SCORES		

Appendix

INCAT Sensory Sum Score (ISS). The ISS ranges from 0 (normal sensation) to 20 (most severe sensory deficit) and is composed of the summation of the following sensation qualities:

- Pinprick arm grade (range 0-4)
- Vibration arm grade (range 0-4)
- Pinprick leg grade (range 0-4)
- Vibration leg grade (range 0-4)
- Two-point discrimination grade (range 0-4)

Pinprick is tested with the sharp end of an esthesiometer, subjects indicate normal or abnormal. Paresthesia, dysesthesia or hyperesthesia are to be scored as abnormal. Normal reference point: face.

Vibration sense is tested using the graduated Rydel-Seiffer tuning fork, measures obtained are compared with the reported normative threshold values.

Pinprick and vibration sense examination take place distal to proximal and only the highest extension of dysfunction of the most affected arm and leg are recorded separately for both qualities.

Pinprick sensation (sites of examination and corresponding grades)		Vibration sensation (sites of examination and corresponding grades)		Two-point discrimination (sites of examination and corresponding grades)
Arms	Legs	Arms	Legs	Index finger ^K
Normal sense 0, at index finger ^A	Normal sense 0, at hallux ^F	Normal sense 0, at index finger ^A	Normal sense 0, at hallux ^F	Normal sense 0, < 4 mm
Abnormal sense 1, at index finger ^B	Abnormal sense 1, at hallux ^G	Abnormal sense 1, at index finger ^B	Abnormal sense 1, at hallux ^G	Abnormal sense 1, 5-9 mm
2, at wrist ^C	2, at ankle ^H	2, at wrist ^C	2, at ankle ^H	2, 10-14 mm
3, at elbow ^D	3, at knee ^I	3, at elbow ^D	3, at knee ^I	3, 15-19 mm
4, at shoulder ^E	4, at groin ^J	4, at shoulder ^E	4, at groin ^J	4, > 20 mm

A,B: index finger (dorsum distal interphalangeal joint); C: ulnar styloid process; D: medial humerus epicondyle; E: acromioclavicular joint; F,G: hallux (dorsum inter-phalangeal joint); H: medial malleolus; I: patella; J: anterior superior iliac spine; K: index finger (ventral side: distal phalanx)

Appendix

Timed 10-meter walking test:

- The patient should be instructed to walk without assistance 10 meters (32.8 feet) and the time is measured for the intermediate 6 meters (19.7 feet) to allow for acceleration and deceleration
 - start timing when the toes of the leading foot crosses the 2-meter mark
 - stop timing when the toes of the leading foot crosses the 8-meter mark
 - assistive devices can be used but should be kept consistent and documented from test to test
- If physical assistance is required to walk, this should not be performed
- The test can be performed at preferred walking speed or fastest speed possible
- The documentation should include the speed tested (preferred vs. fast)
- Three trials have to be performed and the average of the three trials calculated

Set-up (derived from the reference articles):

- measure and mark a 10-meter walkway
- add a mark at 2-meters
- add a mark at 8-meters

Patient Instructions (derived from the reference articles):

Maximum speed trial: “I will say ready, set, go. When I say go, walk as fast as you safely can until I say stop”

Instruction in French: « Je vais vous dire attention, prêt, partez. Lorsque je dis partez, marchez prudemment aussi vite que vous pouvez jusqu'à ce que je vous dise stop. »

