5.7.1.7 Timed 10-meter walk test

In this test the patient is instructed to walk at a comfortable, normal pace for 10 meters. Only the middle 6 m, however, is timed to eliminate the effects of acceleration and deceleration. Start and stop of performance time coincides with the toes of the leading foot crossing the 2-m mark and the 8-m mark, respectively. From these data, the speed may be calculated by dividing the middle 6 m by the time (in seconds) required to walk the 6 m (Wolf 1999).

The reliability of this test is excellent for CMT patients (Solari 2007).

A full instruction for the realisation of the test is displayed in appendix. The test will be performed and result recorded in the CRF at each visit.

5.7.1.8 6-min walk test

The 6MWT is a practical simple test that requires a 30 m (100-ft) hallway but no exercise equipment or advanced training for technicians. This test measures the distance that a patient can quickly walk on a flat, hard surface in a period of 6 minutes. The patient is allowed to self-pace and is encouraged every two minutes by the examiner as he traverses back and forth along a marked walkway.

The reliability and validity of this test has been investigated extensively as it has been used as a functional outcome measure for adults with cardiopulmonary dysfunction. (American Thoracic Society statement: guidelines for the 6MWT, 2002). It has also been used as a functional outcome measure for individuals with multiple sclerosis (Goldman et Al 2008).

The test is more extensively described in appendix and will be performed and recorded in the CRF at each visit.

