“Are you ready to do that? I am going to use this counter to keep track of the number of laps you complete. I will click it each time you turn around at this starting line. Remember that the object is to walk AS FAR AS POSSIBLE for 6 minutes, but don’t run or jog. Start now, or whenever you are ready.”

Standardized Encouragement read in a steady voice:

- After the 1st minute: “You are doing well. You have 5 minutes to go.”
- When the timer shows 4 minutes remaining: “Keep up the good work. You have 4 minutes to go.”
- When the timer shows 3 minutes remaining: “You are doing well. You are halfway done.
- When the timer shows 2 minutes remaining: “Keep up the good work. You have only 2 minutes left.
- When the timer shows 1 minute remaining: “You are doing well. You only have 1 minute to go.

- With 15 seconds to go: “In a moment I’m going to tell you to stop. When I do, just stop right where you are and I will come to you.”
- At 6 minutes: “Stop”

If the participant stops at any time prior, you can say: “You can lean against the wall if you would like; then continue walking whenever you feel able.”

Do not use other words of encouragement (or body language) to influence the patient’s walking speed. Accompany the participant along the walking course, but keep just behind them. Do not lead them.

III. DETAILED INSTRUCTIONS FOR EACH ITEM

Before starting:

Item 1. Pulse: Record beats per minute.

Starting test:

Item 2. Start of 6-minute walk: Record time in hours and minutes. Choose AM or PM.

Immediately following 6MW: Record the following:

Item 3. Pulse: Record beats per minute.

Item 4. Breathlessness: Record participant’s response from 0-10 on the Modified Borg Scale (0=no breathlessness, nothing at all, 0.5=very, very slight, 1=very slight, 2=slight breathlessness, 3=moderate, 4=somewhat severe, 5=severe breathlessness, 6=is between severe breathlessness and very severe breathlessness, 7=very severe breathlessness, 8=between very severe breathlessness and very,very severe breathlessness, 9=very, very severe breathlessness, 10=maximum breathlessness.)

Item 5. Exertion: Record participant’s response from Scale of Perceived Exertion (0=none, 2=very,very light, 3=very light, 4=fairly light, 5=somewhat hard, 6=hard, 7=very hard, 8=very,very hard.

Item 6. Type of course used: Select the type of course used. Record 1 for 30 meters x 2 lengths, 2 for 100 feet x 2 lengths, or 3 for other. If Other, specify in the space provided.

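### The protocol gives conflicting instructions on pace for the 10-meter walk, and the SAP tests the week-48 change without checking that both tests were done at the same pace

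*Protocol*

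**What the plan says.** **Pace, 10-meter walk.** Protocol 5.7.1.7 states: "In this test the patient is instructed to walk at a comfortable, normal pace for 10 meters". It sends the reader to the appendix for the full instructions. The appendix states: "The test can be performed at preferred walking speed or fastest speed possible". The only words to be read to the patient, in English and French, are for a maximum-speed trial: "When I say go, walk as fast as you safely can until I say stop". There is no script for a preferred-speed trial.

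**Constancy.** For walking aids the appendix requires both recording and constancy: "assistive devices can be used but should be kept consistent and documented from test to test". For pace it asks only that the documentation show which of the two speeds was tested. Three trials are averaged at each visit.

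**Analysis.** SAP 10.2 lists the 10-meter time in seconds as a secondary endpoint, whatever the assistance. It defines the change as the week-48 value minus the baseline value and applies a Wilcoxon signed-rank test to all patients together. SAP 3.1 makes the test two-sided at 5%. SAP 2.2 and 3.2 fill a missing week-48 value of a secondary criterion by last observation carried forward (LOCF). None of these sections mentions pace.

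**Setting.** The study is open label, at one site, with 15 patients and no control arm (Protocol 4 and 5.1.1). Protocol 7.1.5 ranks the 10-meter walk second among the clinical endpoints in CIDP and third in anti-MAG and in CMT.

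**6-minute walk.** Protocol 5.7.1.8 says that the patient "is encouraged every two minutes by the examiner". The appendix scripts a prompt after the first minute and then at each further minute, for example "When the timer shows 4 minutes remaining", and forbids other encouragement.

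**The concern.** An examiner who follows 5.7.1.7 and one who reads out the appendix script run different tests. Both comply with the protocol, because the appendix allows either pace. Nothing obliges the site to keep a given patient at one pace from baseline to week 48, and nothing in the SAP would detect a change.

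With a control arm, such a shift might be expected to affect both arms and largely cancel. Here each patient is his or her own only comparator, so a change of pace goes straight into the estimated change. The walk times also have a further use: Protocol 7.1.1 and SAP 1.3 want the endpoints ranked for confirmatory studies, and Protocol 4 wants the results to inform the next sample size. Mixing paces would disturb both the mean change and its standard deviation.

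**Working it through.** The documents state no effect size, variability or power for the walk test, so there is no planned figure to reproduce. The check is a comparison of texts, followed by an illustration on the scale that the SAP uses (seconds and the signed-rank test).

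**Step 1: the texts side by side**

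| Question | Protocol 5.7.1.7 | Protocol appendix | SAP 10.2 |
|---|---|---|---|
| Which pace? | comfortable | preferred or fastest; script for fastest only | not mentioned |
| Same pace at each visit? | not stated | not required; pace documented | not checked |
| Same walking aid? | not stated | required and documented | analysed whatever the assistance |
| If week 48 is missing? | – | – | LOCF (SAP 2.2, 3.2), pace not checked |

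The sentence in the appendix is only an open option when read alone. The contradiction appears when it is read with 5.7.1.7 and the maximum-speed script. The gap in the analysis comes from the second and fourth rows.

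**Step 2: what one change of pace does to one patient**

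Only the middle 6 m is timed, so time = 6 / speed. The documents give neither walking speeds nor the ratio r of fast to comfortable speed. Assumed: comfortable speed 0.8 to 1.2 m/s, r from 1.1 to 1.4.

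- At 1.0 m/s: 6 / 1.0 = 6.00 s at comfortable pace. With r = 1.1, 6 / 1.1 = 5.45 s (change -0.55 s). With r = 1.2, 6 / 1.2 = 5.00 s (-1.00 s). With r = 1.4, 6 / 1.4 = 4.29 s (-1.71 s).
- Over the whole assumed grid the change runs from -0.45 s (1.2 m/s, r = 1.1) to -2.14 s (0.8 m/s, r = 1.4).
- From fast to comfortable the same figures apply with a plus sign.

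**Step 3: what it does to the mean**

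If k of 15 patients change pace in the same direction, the mean moves by (k / 15) × the individual change. With k = 3, 1.0 m/s and r = 1.2: (3 / 15) × (-1.00) = -0.20 s. If changes go both ways, the mean shifts cancel but the spread grows.

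**Step 4: what it does to the planned test**

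If the other patients do not change at all, zeros are dropped and all k changes have the same sign, the exact two-sided p is 2 × (1/2)^k:

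| k | p |
|---|---|
| 2 | 0.50 |
| 3 | 0.25 |
| 5 | 0.0625 |
| 6 | 0.031 |

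In practice every patient varies between visits. A simulation with n = 15 and no drug effect used a median comfortable speed of 1.0 m/s with log-scale SD 0.25 between patients, measurement CV of 5% or 10% at each test, r = 1.1, 1.2 or 1.3, and 3,000 runs per setting. All k patients move from comfortable to fast pace.

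| Patients who change pace | Share of runs with p < 0.05 |
|---|---|
| 0 | 4% to 6% |
| 3 | 7% to 14% |
| 5 | 10% to 39% |
| 8 | 19% to 95% |
| 15 | 65% to 100% |

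A few changes of pace inflate the false-positive rate modestly. A change across the whole site would dominate the result. The documents do not say which row applies.

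**Step 5: the 6-minute walk**

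The body text implies prompts at about 2 and 4 minutes; the script gives them at 1, 2, 3, 4 and 5 minutes. The documents contain nothing from which an effect on distance could be calculated.

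**The case against.** The strongest reply is that the appendix governs. Section 5.7.1.7 refers to it for full instructions, its only script is for maximum speed, and one site with 15 patients probably used one habit throughout. A patient tested at the same pace at every visit has an unbiased change whichever pace it was, and the protocol allows exactly that. This stands as a reason why the risk may be small. It does not remove the risk, because the appendix itself permits either pace and requires constancy for aids but not for pace.

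Second, SAP 2.1 lists changes of method for the MRC score and posturography and none for walking. A reader might infer from those entries that walking pace drifted too, or from the silence that it did not. Neither follows.

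Third, the sizes above are assumed and show one direction only. That is correct. The documents support neither a figure for the ratio nor a number of patients changing pace, and they give no reason to expect drift towards fast rather than towards comfortable. A claim that the walk result is biased towards benefit would go too far.

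Fourth, a reader might extend the point to the 6-minute walk because its two descriptions also differ. That is not supported. The appendix gives a fixed word-for-word script, 5.7.1.8 refers to it for the fuller description, and there is no visible reason why the schedule would differ between baseline and week 48. It is an editorial inconsistency.

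Finally, the endpoint is secondary and exploratory, and the electrophysiological primary endpoint is untouched. That stands and limits the weight of the point.

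**Conclusion.** The point holds for the 10-meter walk. The protocol contradicts itself on pace and does not require one pace per patient, and SAP 10.2 tests the change without checking pace. In an uncontrolled study a within-patient change of pace could therefore pass for benefit or for harm.

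Whether it did is unknown. On assumed values, one change of pace moves a patient's time by about 0.5 to 2.1 s in either direction. With 3 of 15 patients changing in the same direction, the chance of a false significant result rises from about 5% to between 7% and 14%; it becomes large only if many patients change the same way. These figures are illustrations, not estimates for this trial.

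The consequence is confined to one secondary endpoint and to its use in ranking endpoints and planning the next study. No effect on the 6-minute results is claimed.

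**What to change.** **In the SAP, for this trial.** SAP section 1 says that it was signed after all patients had completed, so only the analysis can still change.

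1. In section 10.2, compute and test the 10-meter change only when the baseline value and the week-48 value have the same recorded pace. Apply the same condition to a carried-forward value, using the pace recorded at the visit it comes from.
2. List the remaining pairs with both paces and leave them out of the change and the test.
3. The appendix asks for pace to be documented, but 5.7.1.7 says only that the result goes into the CRF, so pace may not be in the database. If it is not, retrieve it from source documents. If it cannot be retrieved, report the limitation and do not use this test to rank endpoints.

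**In the protocol, for later use.** Reconcile 5.7.1.7 and the appendix to a single pace, supply the script for it, and require it at every visit of a given patient, as is already required for walking aids. Which pace to choose is for the sponsor and the investigator.

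**Editorial.** Align the encouragement wording in 5.7.1.8 with the appendix script for the 6-minute walk.

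**Cost.** One condition and one listing in the SAP, possibly a look at source records, and the loss of a few pairs. With five patients per disease group even a few lost pairs will show, so the number excluded should be reported by group.
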